### 10.1 Interim Analysis

#### 10.1.1 General Consideration

Refer to Section 7.5 for the timing of the IA. General considerations, reporting conventions, and analysis methods specified for the final analysis apply to the IA, unless otherwise specified.

For the IA purpose, the **treatment-emergent (TE) period** will include the time from the first dose of study drug in the Treatment Period until 28 days after the last dose of study drug, or the study participation end date, or the IA data cutoff date, whichever occurs first.

#### 10.1.2 Background Characteristics

##### 10.1.2.1 Subject Disposition

The number of subjects in the following categories will be summarized:

- All Subjects Set
- Interim Full Analysis Set
- IA Safety Set
- Safety Set
- Randomized
- Randomized but not dosed

The number and percentage (based on the iFAS) of subjects in each of the following disposition categories will be summarized by treatment group and overall:

- Completed Week 4 Visit
- Prematurely discontinued treatment before Week 4 Visit and the reason for discontinuation
- Completed Week 12 Visit
- Prematurely discontinued treatment before Week 12 Visit and the reason for discontinuation
- Completed treatment
- Prematurely discontinued treatment and the reason for discontinuation
- Completed study
- Prematurely discontinued the study and the reason for discontinuation
- Rollover to open-label study

A listing will be provided for subjects who discontinued treatment or who discontinued study with reasons for discontinuation.

#### **10.1.2.2 Demographics and Baseline Characteristics**

The same demographics and baseline characteristics specified in Section 9.2.2 will be summarized based on the iFAS.

#### **10.1.2.3 Study Drug Exposure**

For the purpose of the IA, the study drug exposure will be calculated using the same approach specified in Section 9.2.5. For subjects who are still on study drug at the IA data cutoff date, the IA data cutoff date will be used as the last dose date for the exposure calculation.

Exposure summaries will be provided for subjects in the IA Safety Set as well as for subjects in the Safety Set who had been on-study for  $\geq 12$  weeks, and will be presented by treatment group and overall.

#### **10.1.3 Efficacy Analysis**

All efficacy analyses described in this section will be based on the iFAS, unless otherwise specified.

##### **10.1.3.1 Analysis of Primary Efficacy Variable**

The analysis of the primary efficacy variable of absolute change in ppFEV1 from baseline at Week 4 will be performed using an MMRM with change from baseline at Day 15 and Week 4 as

the dependent variable. The model will include treatment group, visit, and treatment by visit interaction as fixed effects, with continuous baseline ppFEV1, age at screening (<18 versus ≥18 years of age) and sex (male versus female) as covariates. The model will be estimated using restricted maximum likelihood. Denominator degrees of freedom for the *F*-test for fixed effects will be estimated using the Kenward-Roger approximation. An unstructured covariance structure will be used to model the within-subject errors. If the model estimation does not converge, a compound symmetry covariance structure will be used instead. Conditional on the observed data and covariates, missing data will be assumed to be missing at random; consequently, no imputation of missing data will be performed.

[REDACTED]

[REDACTED]

- [REDACTED]
- [REDACTED]
- [REDACTED]
- [REDACTED]

### 10.1.3.2 Analysis of Key Secondary Efficacy Variable

The following key secondary efficacy variables defined in Section 9.3.2.1 will be analyzed during the IA using an ANCOVA model:

- Absolute change in SwCl from baseline at Week 4
- Absolute change in CFQ-R respiratory domain score from baseline at Week 4

The model will use the change from baseline value at Week 4 as the dependent variable and include treatment group as fixed effects with continuous baseline ppFEV1, age at screening (<18 versus ≥18 years of age), and sex (male versus female) as covariates. The estimated treatment difference at Week 4, the adjusted means with 2-sided 95% confidence intervals and nominal 2-sided *P* values will be provided.

[figure not shown]
Analyses of other efficacy and/or pharmacodynamic variables may be performed if the data are deemed sufficient.

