**12 STATISTICAL AND ANALYTICAL PLANS**

This section presents a summary of the planned analyses for this protocol. Statistical analysis details will be provided in the statistical analysis plan (SAP), and clinical pharmacologic analysis details will be provided in the clinical pharmacology analysis plan (CPAP), both of which will be finalized before the clinical data lock for the study and treatment unblinding.

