#### 12.3.3.3.2 Analysis of Key Secondary Variables

The following key secondary efficacy and pharmacodynamic variables will be analyzed during the IA using an Analysis of Covariance (ANCOVA) model and nominal *P* value will be provided for descriptive purpose:

1. Absolute change in SwCl from baseline at Week 4
2. Absolute change in CFQ-R respiratory domain score from baseline at Week 4

The model will use the change from baseline value at Week 4 as the dependent variable and include treatment group as fixed effects with continuous baseline ppFEV1, age at screening (<18 versus ≥18 years of age), and sex (male versus female) as covariates.

Additional details will be provided in the SAP.

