## 4 INTRODUCTION

This statistical analysis plan (SAP) for the interim and final analysis is based on the most recent approved clinical study protocol (CSP), electronic case report form (eCRF), and eCRF completion guidelines.

This SAP (Methods) documents the planned statistical analyses of efficacy endpoints and safety endpoints for the interim analysis (IA) and the final analysis. [REDACTED]

The pharmacokinetic (PK) and pharmacodynamic (PD) characteristics of VX-659 in the population heterozygous for the *F508del* mutation and a minimal function mutation will also be evaluated in the study. Selected analyses related to sweat chloride will be documented in this SAP, other PK and PD analyses will be documented separately in the clinical pharmacology analysis plan (CPAP) for the study.

This SAP (Methods) will be finalized and approved prior to IA data lock and treatment unblinding for the IA. Any revisions to the approved SAP will be documented and approved in an amendment to the SAP.

The Vertex Biometrics Department will perform the statistical analysis for the final analysis and prepare the analysis package for the IA; SAS (Version 9.4 or higher) will be used to generate all statistical outputs (tables, figures, listings, and datasets). ICON Clinical Research Limited (ICON), appointed as the independent biostatistician, will perform the IA according to the DMC SAP and present the results to the DMC. If the DMC declares that the study has crossed the efficacy boundary, a limited Vertex unblinded team (independent of the study team) may be unblinded to the study and prepare for regulatory submission(s) based on the IA.

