**Table 7-2 The Alpha Spending with Various N at the Interim Analysis**

Sample Size in interim Full Analysis Set (information fraction)	Alpha at IA ( $\alpha_0$ )	Alpha at Final ( $\alpha_1$ )
140 (39%)	0.0440	0.01
180 (50%)	0.0451	0.01
220 (61%)	0.0465	0.01
260 (72%)	0.0480	0.01
300 (83%)	0.0492	0.01

If the *P* value for the primary endpoint at the IA is less than  $\alpha_0$ , then the efficacy boundary has been crossed. If the DMC declares that the study has crossed the efficacy boundary, then the study may be unblinded to a limited Vertex team to prepare regulatory submission(s). Members of the limited Vertex unblinded team will not be involved in or influence the conduct of the remaining part of the study to protect the integrity of the study.

If the *P* value fails to cross the efficacy boundary during the IA (i.e., *P* value  $\geq \alpha_0$ ), then the primary endpoint of absolute change in ppFEV1 from baseline at Week 4 will be tested after all subjects complete study participation at an alpha of 0.01.

Selected key secondary endpoints will be analyzed during the IA with nominal *P* value provided for descriptive purpose (see Section 10.1.3.2).

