### 9.1 General Considerations

The Schedule of Assessments is provided in Section 3 of CSP. The precision standards for reporting safety and efficacy variables are provided in an internal Biometrics document that specifies the programming rules including the precision for derived variables.

**Continuous variables** will be summarized using the following descriptive summary statistics: the number of subjects (n), mean, SD, median, minimum value (min), and maximum value (max).

**Categorical variables** will be summarized using counts and percentages. Percentages will be presented to 1 decimal place.

**Baseline value**, unless otherwise specified, is defined as the most recent non-missing measurement (scheduled or unscheduled) collected before the first dose of study drug in the Treatment Period.

**Absolute change** from baseline will be calculated as post-baseline value - baseline value.

**Relative change** from baseline will be calculated as (post-baseline value - baseline value)/baseline value.

**Treatment-emergent (TE) period** will include the time from the first dose of study drug in the Treatment Period until 28 days after the last dose of study drug or to the completion of study participation, whichever occurs first.

Completion of study participation for each individual subject is defined as one of the following:

- For subjects who complete the Treatment Period and enter an open-label study within 28 days of the Week 24 Visit: the Week 24 Visit
- For subjects who complete the Treatment Period and do not enter an open-label study within 28 days of the Week 24 Visit: the Safety Follow-up Visit
- For subjects who prematurely discontinue study drug treatment but do not withdraw consent (and assent, as applicable): the latest of the Week 24 Visit, Early Termination of Treatment Visit, or Safety Follow-up Visit (if required)
- For subjects who withdraw consent or assent: date of withdrawal of consent or assent, whichever is earlier (CSP Section 9.9)

If subjects are lost to follow-up (CSP Section 9.1.5), the date of completion of study participation will be defined as the date of the last contact.

**Unscheduled visits:** Unscheduled visit measurements will be included in analysis as follows:

- 1) In scheduled visit windows per specified visit windowing rules
- 2) In the derivation of baseline and last on-treatment measurements

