### **9.2.2 Demographics and Baseline Characteristics**

Demographics and baseline characteristics will be summarized by treatment group and overall based on the FAS.

Demographic data will include the following:

- Age at baseline (in years)
- Sex (male, female)
- Ethnicity (Hispanic or Latino, not Hispanic or Latino, and not collected per local regulations)
- Race (White, Black or African American, Asian, American Indian or Alaska Native, Native Hawaiian or Other Pacific Islander, Other, and not collected per local regulations)
- Geographic region (North America, Europe [including Israel and Australia])

Baseline characteristics will include the following:

- Weight (kg)
- Height (cm)
- BMI (kg/m^2)
- BMI z-score (for subjects  $\leq 20$  years old at Baseline)

Stratification categories (in addition to sex) will include the following:

- Age at the Screening Visit (<18, and  $\geq 18$  years)
- ppFEV1 determined during the Screening Period (<70, and  $\geq 70$ )

Disease characteristics will include the following:

- ppFEV1 at baseline (<40,  $\geq 40$  to <70,  $\geq 70$  to  $\leq 90$ , and >90)
- ppFEV1 at baseline (continuous)

- Sweat chloride at baseline (continuous)
- CFQ-R respiratory domain score at baseline (continuous)
- Prior use of dornase alfa (Yes, No)
- Prior use of azithromycin (Yes, No)
- Prior use of inhaled antibiotic (Yes, No)
- Prior use of any bronchodilator (Yes, No)
- Prior use of any inhaled bronchodilator (Yes, No)
- Prior use of any inhaled hypertonic saline (Yes, No)
- Prior use of any inhaled corticosteroids (Yes, No)
- Infection with *Pseudomonas aeruginosa* within 2 years prior to screening (Positive, Negative)

In addition, data listings will also be provided for:

- Informed consent;
- Inclusion/Exclusion criteria violation for subjects with any such violations.

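### The interim SwCl and CFQ-R models leave out the endpoint's own baseline, and the final SwCl, CFQ-R, BMI and weight models do not say whether they include it

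*SAP*

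**What the plan says.** **Interim.** SAP 10.1.3.2 analyses change from baseline at Week 4 in SwCl and in CFQ-R respiratory domain by ANCOVA. The models "include treatment group as fixed effects with continuous baseline ppFEV 1 , age at screening" group, and sex. Protocol 12.3.3.3.2 carries the same list and closes with "Additional details will be provided in the SAP". Baseline SwCl and baseline CFQ-R are in neither list. The role of these analyses is limited: "Selected key secondary endpoints will be analyzed during the IA with nominal *P* value provided for descriptive purpose" (SAP 7.5). The interim primary model (SAP 10.1.3.1) does adjust for baseline ppFEV1, its own baseline.

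**Final.** SAP 9.3.2.2 describes the MMRMs for SwCl, CFQ-R and BMI, and SAP 9.3.3.2 those for BMI z-score and weight, only as similar to the primary analysis. The primary model (SAP 9.3.1.2) has baseline ppFEV1, age group and sex as covariates. The one covariate change spelled out is the removal of age group for BMI z-score.

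**Outcome scale.** Absolute change "from baseline will be calculated as post-baseline value - baseline value" (SAP 9.1).

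**Availability of the baselines.** SAP 9.2.2 already summarizes them, for example "Sweat chloride at baseline (continuous"), along with CFQ-R, weight, BMI and BMI z-score.

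**The concern.** A change score subtracts the whole baseline value. Unless the model also contains that baseline, it uses a slope of 1 where the data may support a smaller one. Two things follow. The residual variance is larger than it need be. And a chance baseline difference D between arms is over-corrected, by (1 − r)·D under equal variances, where r is the baseline-to-visit correlation.

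At the interim the omission is explicit. For the final analysis it is a question of reading. In the primary model, baseline ppFEV1 is both a severity covariate and the endpoint's own baseline, so a similar model could keep ppFEV1, replace it with the endpoint's baseline, or use both. The interim lists, and the BMI z-score text that removes only age group, point towards carrying ppFEV1 over. Calling only the ppFEV1-through-Week-24 model exactly the same as the primary fits either reading.

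The wording governs five of the seven key secondary endpoints, which are steps 3 to 7 of the 0.05 hierarchy in SAP 9.3.2.3 (SwCl and CFQ-R through Week 24 and at Week 4, and BMI at Week 24). It also governs two other secondary endpoints, BMI z-score and weight.

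**Working it through.** **The plan's nearest figure.** The documents state no power, SD or correlation for SwCl, CFQ-R, BMI or weight. The nearest figure is the interim power for ppFEV1 in SAP 7.2 (SD 7, difference 5.0, 70 per arm, 5% dropout, alpha 0.044):

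- n = 70 × 0.95 = 66.5 per arm
- SE = 7·√(2/66.5) = 1.214, and 5.0/1.214 = 4.119
- 4.119 − 2.014 = 2.105, so power is 0.982 (0.981 with the noncentral t), against a stated 98%

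It reproduces. It concerns a model that already includes its own baseline and is not in question.

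**Inputs (all assumptions).** Baseline SD is 1 in both arms; post-baseline SDs are s_c (placebo) and s_t (treated). r is the baseline-to-visit correlation, and p ≥ r the correlation between post-baseline visits. m is the number of visits averaged: 1 for a single visit, 4 for SwCl and 5 for CFQ-R through Week 24. Baseline ppFEV1 is taken to explain little of the change. Allocation is 1:1.

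**Formulas.** Per-arm variance of the visit mean: V = s²(1 + (m−1)p)/m. Pooled slope: b = r(s_c + s_t)/2. Summed over arms, the variance of the mean change is:

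- without own baseline: ΣV + 2 − 4b
- with own baseline: ΣV − 2b²

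The difference is 2(1 − b)², which is never negative and is zero at b = 1. The SE excess from omission is (with/without)^(−1/2) − 1.

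**One visit, equal SDs.** The ratio with/without is (2 − 2r²)/(4 − 4r) = (1 + r)/2.

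| r | variance ratio | SE excess without own baseline |
|---|---|---|
| 0.5 | 0.75 | 15.5% |
| 0.7 | 0.85 | 8.5% |
| 0.9 | 0.95 | 2.6% |
| 0.95 | 0.975 | 1.3% |

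**Average over visits, equal SDs.** For example, with m = 4 and r = p = 0.5: V = 2.5/4 = 0.625 and ΣV = 1.25; without = 1.25 and with = 0.75; ratio 0.600.

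| r | p | m = 4 (SwCl) | m = 5 (CFQ-R) |
|---|---|---|---|
| 0.5 | 0.5 | 0.600, 29.1% | 0.583, 30.9% |
| 0.5 | 0.8 | 0.706, 19.0% | 0.702, 19.3% |
| 0.7 | 0.7 | 0.760, 14.7% | 0.750, 15.5% |
| 0.7 | 0.8 | 0.800, 11.8% | 0.795, 12.1% |

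As p approaches 1 these fall to the one-visit values of 15.5% and 8.5%.

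**Unequal SDs, one visit (s_c = 1).**

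| s_t | r = 0.5 | r = 0.7 | r = 0.9 |
|---|---|---|---|
| 1.3 | 8.5% | 2.7% | 0.2% |
| 0.7 | 25.9% | 19.1% | 16.0% |

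**Chance imbalance of one SE, equal variances.** The over-correction is (1 − r)·√(2/n) baseline SDs.

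- Final, n = 180 × 0.9 = 162 per arm: 0.5·√(2/162) = 0.056 at r = 0.5; 0.05·√(2/162) = 0.006 at r = 0.95.
- Interim, n = 70 per arm: 0.5·√(2/70) = 0.085 at r = 0.5; 0.1·√(2/70) = 0.017 at r = 0.9.

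**Simulation.** With 162 per arm and 4,000 runs per setting, the SE excess was 14.7% (m = 1, r = 0.5), 28.0% (m = 4, r = p = 0.5), 19.1% (m = 4, r = 0.5, p = 0.8), and 8.3% and 0.2% (m = 1, s_t = 1.3, r = 0.5 and 0.9). Type I error without own baseline was 4.35% to 5.65% over 11 settings (Monte Carlo SE 0.34 points), so validity is not at issue. At about interim size (66 per arm, with baseline ppFEV1, age and sex in the model and ppFEV1 correlated 0.3 with own baseline), both models were unbiased: means were 0.495 to 0.506 for a true effect of 0.5. Adding own baseline multiplied the SE by 0.815, 0.888 and 0.935 at r = 0.3, 0.5 and 0.7.

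**The case against.** The covariates are not arbitrary. Randomization is stratified by ppFEV1, age and sex (SAP 7.3), and the same three variables, with ppFEV1 continuous, adjust every model whose covariates are listed: the primary MMRM, negative binomial, Cox and interim models. That is a coherent pre-specified set, identical in protocol and SAP. It does not argue against own baseline, though, because the three variables stay in the model when it is added.

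Several objections stand as limits:

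- The interim results are descriptive and drive no decision. The boundary depends on ppFEV1 alone.
- The final-analysis loss exists only if the similar models exclude own baseline.
- The SAP text between Appendix F and the later section headed 5.2 Efficacy Analysis was not available here. That later section adds model detail for event counts, so the missing text could list these covariates. If it does, only the interim point remains.
- The gain may be close to nil, and for BMI and weight it is probably small if r is around 0.95 or higher.
- No power shortfall is shown. These endpoints are tested formally only if PEx, second in the hierarchy with about 80% stated power, succeeds.

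Finally, adding a covariate would make the SAP differ from a list printed in the protocol. That is true, but the protocol leaves such matters to the SAP: "Statistical analysis details will be provided in the statistical analysis plan (SAP"). The SAP already departs once in this way, by dropping age group for BMI z-score where protocol 12.3.3.1.2 does not.

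**Conclusion.** The point holds as an inexpensive improvement, not as the correction of an invalid analysis. The interim omission is plain in both documents, and the ambiguity in the final models is real on the text available. Under the assumed correlations, leaving out own baseline could cost SwCl and CFQ-R a worthwhile amount of precision. For BMI and weight the benefit is mainly clarity. With 1:1 allocation the large-sample gain is never negative, so there is little to set against it. No trial conclusion is shown to change. Confidence in the size is moderate, because every correlation and SD ratio is assumed.

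**What to change.** Change the SAP only, before interim data lock:

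1. In SAP 9.3.2.2, 9.3.3.2 and 10.1.3.2, list each model's covariates in full in place of the reference to a similar model.
2. Include the continuous baseline of that endpoint in addition to the covariates now planned. The BMI z-score model still omits age group.
3. Make the same choice at the interim and the final analysis.
4. In 10.1.3.2, note that own baseline is added to the list in protocol 12.3.3.3.2.

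Timing follows the SAP's own rule: "This SAP (Methods) will be finalized and approved prior to IA data lock and treatment unblinding for the IA". If it is already approved, an amendment is needed: "Any revisions to the approved SAP will be documented and approved in an amendment to the SAP". The cost is wording and one degree of freedom per model. No new data are needed, and no protocol amendment, because the protocol defers analysis details to the SAP.

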### 10.1.3.3 Summary of Efficacy Variables

The raw and change from baseline in ppFEV1, SwCl and CFQ-R will be summarized descriptively (n, mean, SD, median, minimum, and maximum) at baseline and post-baseline visits. For the IA purpose, a visit will be included in the summary if there are ≥20 subjects with available data from each treatment group at that visit.

#### **10.1.4 Safety Analysis**

Safety analyses specified in Section 9.4 will be performed during the IA based on the IA Safety Set.

#### **10.2 DMC Analysis**

The DMC will conduct planned safety/efficacy review(s) of study data as outlined in the DMC charter. For the open session of each DMC meeting, selected tables will be presented for the overall treatment group based on the blinded data. For the closed session, the presentation will be by treatment group based on the unblinded data (generated by the independent biostatistician).

The timing of DMC meetings is outlined in Table 10-1.

**Table 10-1 DMC Meeting Schedule**

Meeting	Timing
Organizational	Teleconference prior to start of the study
First Planned Review	After $\geq 50$ subjects have completed Week 4
Second Planned Review	Interim analysis of safety and efficacy after $\geq 140$ subjects have completed the Week 4 visit and after $\geq 100$ subjects have completed the Week 12 visit.
Ad-hoc	Teleconference on an as-needed basis

### **10.2.1 DMC Safety/Efficacy Review**

To protect the integrity of the treatment assignment and study data, the following steps for the flow of data will be executed for the DMC review:

1. The Vertex Biometrics Department will prepare the SAS codes, SDTM/ADaM data sets, and blinded outputs (tables, figures and listings) of safety data using dummy treatment codes, dummy (unrestricted) spirometry data, and dummy (unrestricted) sweat chloride data;
2. The IWRS vendor, Bracket, will provide the unblinded treatment codes to the independent biostatistician via a secure file transfer protocol, the independent biostatistician will verify the treatment assignment against the randomization list generated by Cytel;
3. The spirometry vendor will provide the restricted spirometry data directly to the independent biostatistician, via a secure file transfer protocol;
4. The sweat chloride vendor will provide the restricted sweat chloride data directly to independent biostatistician, via a secure file transfer protocol;
5. Independent biostatistician will generate the unblinded outputs (tables, figures and listings) and provide them directly to the DMC team for their review, via a secure file transfer protocol.
6. The Vertex Biometrics Department will generate any blinded outputs (tables, figures and listings), for the open sessions of the DMC meetings, as applicable.

